### **19.3 Sample Size Justification**

The sample size was based on preliminary data gathered at Roswell Park on patients and employees. The values were similar between the two study groups. The Ct values collected at baseline for n=20 patients and employees had an average of 24.1 log2 copies with a standard deviation of 6.5. The standard deviations after baseline was approximately 4.5 as the Ct values increased. The preliminary estimate for the AUC based on our pilot data is 130 (log2 copies) x day, which is the basis for our null hypothesis. The between time point correlation was estimated to be approximately rho=0.3. Given n=10 subjects we will be able to detect and increase in the AUC to an average of 144 (log2 copies) x day (efficacy) or greater than our assumed institutional benchmark of 130 (log2 copies) x day at power=0.80 and alpha=0.05(one-sided). We simplified this calculation assuming no censoring, which will be accounted for in the final analysis and assumed a compound symmetry covariance structure with the correlation estimate described above.

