## **2.6 Overall Impact**

Our study focuses on patients with cancer, but knowledge gained about safety and immunologic correlates is expected to be applicable to other patients at high risk for COVID-19-related morbidity and mortality as well as to future viral pandemics. Using each patient's baseline nasopharyngeal viral load, we will evaluate to what extent the study regimen reduces viral load relative to supportive care only. Assessment of nasopharyngeal viral load at multiple time points will enable evaluation of early and long-term effects of the study regimen in controlling viral replication. A reduction in nasopharyngeal viral load by PCR may also reflect reduced likelihood of transmission of virus to others. As described in the Statistical Plan (Section 19), the study is non-randomized and each patient will serve as their own control regarding baseline, on-treatment, and post-treatment nasopharyngeal viral load. In addition, comparisons will be made with historical controls in which Roswell Park patients with COVID-19 were treated with standard of care and longitudinal viral load was monitored as standard of care. As described in the demonstration of safety of this regimen and reduction of nasopharyngeal viral load will establish the foundation for a larger randomized trial powered for clinical efficacy, such as reduction in respiratory failure and mortality.

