Our study will enroll patients with cancer with varying comorbidities and levels of COVID-19 severity. For outpatients with COVID-19 at high risk for severe complications based on age and co-morbidities, a monoclonal antibody cocktail (e.g. Regeneron's combination of casirivimab and imdevimab) is standard of care. In patients with more severe COVID-19 who are hospitalized and require supplemental oxygen, therapy is focused on controlling inflammatory injury. Dexamethasone was associated with a survival benefit and will be administered to all patients who meet criteria for this agent. Other anti-inflammatory agents such as IL-6-targeting agents and baricitinib can also be of value, although their benefit when added to corticosteroids is unclear. The antiviral agent, remdesivir, is of unclear value based on conflicting data; at best it shortens the duration of illness but doesn't have a survival benefit. At Roswell, we routinely administer combination dexamethasone and remdesivir to inpatients with significant COVID-19, and will do so for patients enrolled in this protocol unless there is a clinical contraindication to receiving either agent. The data on convalescent plasma is also contradictory, but plasma with high neutralizing titers against the viral Spike protein is likely to be of value. We do not know the effect of these standard of care regimens on nasopharyngeal viral load in patients with cancer. In addition, since these regimens are often administered concurrently, it's difficult to delineate the effect of a specific drug on viral load. Based on our experience at Roswell Park, the nasopharyngeal viral load in some

Roswell Park Protocol No.: I-659920

immunocompromised patients with cancer (e.g. stem cell transplant recipients and patients receiving B-cell-depleting agents), has persisted for several weeks despite receiving combinations of these agents (e.g. remdesivir and dexamethasone, often in combination with convalescent plasma). The standard of care for COVID-19 changes over time. Regarding the current protocol, the study regimen will be added to what in our judgment is the best standard of care regardless of outpatient or inpatient status.

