### **3 INCLUSION AND EXCLUSION CRITERIA**

#### **3.1 Inclusion Criteria (Main Cohort)**

To be included in this study, participants must meet the following criteria:

- 1 Patients with cancer, with the exception of patients with active acute leukemia and allogeneic hematopoietic stem cell transplant recipients. Patients may be on active therapy or received therapy (e.g., chemotherapy, radiation, or surgery) within 7 years. Patients with active cancer who have not yet been treated (e.g. newly diagnosed cancer or early stage MDS or CLL) are eligible. Basal cell cancer and carcinoma in situ treated with local excision alone do not qualify for inclusion.
- 2 Presence of symptomatic infection, defined by fever ( $T \geq 38.0^{\circ}\text{C}$ ) OR respiratory symptoms (cough, nasal congestion, or shortness of breath), OR lung infiltrates on chest X-ray or CT imaging, Diagnosis of COVID-19 is based on PCR testing of respiratory samples.
- 3 Age equal to  $\geq 18$  years or older (children are excluded because COVID-19 typically has a milder course in children, and lack of safety data of this regimen in children).
- 4 Laboratory evaluation:
  - Platelet  $\geq 75,000/\mu\text{L}$
  - Hemoglobin  $\geq 9 \text{ g/dL}$
  - Hematocrit  $\geq 27\%$
  - Absolute Neutrophil Count (ANC)  $\geq 1000/\mu\text{L}$
  - Creatinine clearance  $\geq 50 \text{ mL/min}$  (Cockcroft-Gault Equation—note: plasma creatine instead of serum is used at Roswell Park)
  - Total bilirubin  $\leq 2 \times$  institutional ULN
  - AST (plasma) and ALT(plasma)  $\leq 2 \times$  institutional ULN
  - Plasma amylase and lipase  $\leq 2 \times$  institutional ULN
- 5 In the absence of COVID-19, a life expectancy of 6 months is expected.
- 6 Participant must understand the investigational nature of this study and sign an Independent Ethics Committee/Institutional Review Board approved written informed consent form prior to receiving any study related procedure.

**NOTE:** For blood chemistry labs, Roswell Park clinical blood chemistries are performed on plasma unless otherwise indicated.

Roswell Park Protocol No.: I-659920

Refer to **Appendix D** for the Investigator Study Eligibility Verification Form (Main Cohort): Inclusion Criteria.

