## **19 STATISTICAL PLAN**

### **19.1 Study Design/Endpoints**

This is prospective Phase I/IIa trial basket trial of i.v. rintatolimod administered with or without i.v. IFN $\alpha$  (INTRON $\circledR$  A) in two cohorts of patients: Main Cohort and Expansion Cohort. Only Main Cohort subjects will participate in the Phase I 3+3 portion of this study. The Expansion

Roswell Park Protocol No.: I-659920

Cohort will consist of rintatolimod without IFN $\alpha$ . Neither cohort is randomized. The kinetics of nasopharyngeal viral load will be assessed based on baseline values and on treatment and EOT values. In the Expansion Cohort, the kinetics of nasopharyngeal viral load will be compared with historical controls consisting of Roswell Park patients with COVID-19 of varying severity. All patients will receive best available standard of care in addition to study drug regimens.

**Phase I.** The Phase I component of the protocol consists of a 3+3 design with four dose levels of IFN $\alpha$  (0, 5 MU/M, 10 MU/M and 20 MU/M ) and fixed dose rintatolimod (200 mg per day) administered on Days 1 and 3. The sample size for the Phase I trial may range from n=3 to 24.

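### The Phase IIa null value of 130 comes from a pilot of patients and employees, with no stated restriction to people who meet the Main Cohort criteria

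*Combined protocol and SAP*

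**What the plan says.** Section 19.2.2 sets the primary efficacy test as a one-sided test, at 0.05, of a mean AUC of 130 against a larger value. Section 19.3 gives the origin of that number: "preliminary estimate for the AUC based on our pilot data is 130 (log2 copies) x day, which is the basis for our null hypothesis". It describes the pilot in two sentences: "The sample size was based on preliminary data gathered at Roswell Park on patients and employees", and "The Ct values collected at baseline for n=20 patients and employees had an average of 24.1 log2 copies with a standard deviation of 6.5". On comparability it says only: "The values were similar between the two study groups".

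The people tested against 130 are the 10 Phase IIa subjects of the Main Cohort. Inclusion criterion 1 in 3.1 is "Patients with cancer, with the exception of patients with active acute leukemia and allogeneic hematopoietic stem cell transplant recipients". They must also have symptomatic infection and meet laboratory limits (3.1), must not have severe COVID-19 (3.2), and all receive best available standard of care (section 10). Section 19.4 confirms that nothing is randomized.

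Two other places describe comparators. Section 2.6 says "comparisons will be made with historical controls in which Roswell Park patients with COVID-19 were treated with standard of care", with viral load followed over time. Section 19.1 says the Expansion Cohort will be compared with "historical controls consisting of Roswell Park patients with COVID-19 of varying severity". Neither section states an eligibility filter, matching or adjustment.

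**The concern.** In a single-arm test against a fixed value, the people behind that value are the control group. An employee need not have cancer, need not satisfy the symptom, laboratory or severity limits, and is not stated to have received the care every trial patient gets. The difference between observed AUC and 130 then combines any drug effect with any difference between the pilot population and the trial population.

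The error could go either way. If eligible patients on standard of care alone would average above 130, the test rejects too often under no drug effect. If they would average below 130, a real effect can be missed. Section 2.6 also concedes: "We do not know the effect of these standard of care regimens on nasopharyngeal viral load in patients with cancer". The plan therefore has no stated basis for assuming that a mixed pilot gives the right null value.

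**Working it through.** **Inputs.** From 19.3: n = 20 (given only for baseline Ct), baseline SD 6.5, later SDs about 4.5, correlation 0.3 with compound symmetry, n = 10 treated, 144 against 130 (difference 14), power 0.80, one-sided alpha 0.05. From the text of 19.2.2: visits at Days 0, 3, 7 and 14. The formula there adds Day 30; the text's four visits are used here. The patient/employee split is not given, so 10/10 and 15/5 are assumed, as is an AUC from each of the 20.

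**SD of the AUC from the stated inputs.** The trapezoid weights are (1.5, 3.5, 5.5, 3.5). Weight times SD gives (9.75, 15.75, 24.75, 15.75), with sum 66.0 and sum of squares 1203.75.

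Var(AUC) = 0.7 × 1203.75 + 0.3 × 66.0² = 842.6 + 1306.8 = 2149.4, so SD = 46.4.

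**The plan's own figure.** With SD 46.4, n = 10 and difference 14, the power of the one-sided t test is 0.22, not 0.80. The stated 0.80 needs an SD of about 16.4. Both SDs are carried forward, because the documents do not show which one governs the pilot.

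**What the similarity statement could exclude.** The 95% half-width for a patient-minus-employee difference is t(18) × SD × √(1/a + 1/b), with t(18) = 2.101.

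| SD | Split | SE | Half-width |
|---|---|---|---|
| 16.4 | 10/10 | 7.33 | 15.4 |
| 16.4 | 15/5 | 8.47 | 17.8 |
| 46.4 | 10/10 | 20.75 | 43.6 |
| 46.4 | 15/5 | 23.96 | 50.3 |

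Each is larger than 14. As a multiple of the target, they run from 15.4/14 = 1.1 to 50.3/14 = 3.6.

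**Effect of a mismatch on the test.** The documents give no mismatch, so its size is assumed. If eligible patients on standard of care alone averaged 7 above 130, the real one-sided type I error would be 0.35 (SD 16.4) or 0.11 (SD 46.4). If they averaged 7 below, a true gain of 14 would leave only 7 above 130, and power would be the same 0.35 or 0.11. Over 14 days, 14 units is 14/14 = 1.0 Ct cycle on average, so a population difference of one cycle equals the whole target effect.

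**Precision of 130 itself.** With 20 AUCs, the 95% margin around the pilot mean would be 2.093 × 16.4/√20 = ±7.7, or 2.093 × 46.4/√20 = ±21.7. The test treats 130 as known.

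**Caveat on scale.** A Ct held flat at 24.1 for 14 days gives 24.1 × 14 = 337, and 19.3 says Ct rose. So 130 does not fit a Day 0–14 Ct area, and comparing half-widths on that scale with a 14-unit target is only indicative.

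**The case against.** The strongest reply is that the documents do not show the benchmark to be wrong. They are silent on who the pilot subjects were, and the one relevant statement is that values were similar. Section 19.3 calls the 130 preliminary, and 2.6 presents the trial as groundwork for a randomized one. This stands in part: the supportable claim is that no restriction is stated, not that pilot subjects were ineligible or untreated. But the similarity statement has no figures and, read naturally, compares patients with employees rather than either group with eligible patients.

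A reader might infer four stronger things that the documents do not support.

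- That the pilot could hide a difference of three times the target. That holds only with SD 46.4, which does not reproduce the stated power. With SD 16.4 the multiple is about 1.1 to 1.3.
- That the protocol expects cancer patients in general to clear virus more slowly. Section 2.6 reports persistence in some immunocompromised patients, giving stem cell transplant and B-cell depletion as examples. Allogeneic recipients are excluded from the Main Cohort.
- That 19.3 flatly contradicts 2.6. Section 19.1 speaks of institutional benchmarks for Phase IIa and of historical controls for the Expansion Cohort, so these may be two different comparators.
- That the Expansion comparator has the same fault. It consists of patients, 2.6 describes historical controls as on standard of care with viral load followed, and the cohort itself spans a wide range of severity.

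**Conclusion.** The point holds for the Phase IIa primary test. Its null value comes from a pilot that includes employees, and no eligibility, cancer or standard-of-care condition is stated for it. The similarity statement cannot carry the weight put on it: under the assumed 10/10 and 15/5 splits of 20 AUCs, differences of about 15 to 18 units (SD 16.4) or 44 to 50 units (SD 46.4) would be compatible with groups that look alike, against a target of 14. Those figures rest on the assumed splits, on all 20 subjects having contributed AUCs, and on a scale for 130 that the plan leaves unclear. Neither the size nor the direction of any bias can be found from the documents.

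The Expansion Cohort point is secondary. Varying severity on both sides is not itself a fault; the gap is that no stated filter or adjustment keeps the mix comparable.

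**What to change.** In 19.2.2 and 19.3, derive the Phase IIa benchmark from institutional patients who meet 3.1 and 3.2 as far as records allow, received standard of care, and have a detectable baseline swab and serial swabs. Fix that selection before Phase IIa data are read. State the number of controls and the benchmark's confidence interval. Report the test against the employee-inclusive 130 only as a sensitivity analysis.

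For the Expansion Cohort, apply 3.3 and 3.4 to the historical controls, and restrict, match or adjust for baseline oxygen or ventilation status and transplant status.

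The cost is SAP wording and a new query of institutional records; 2.6 indicates that standard-of-care patients with serial viral loads exist, but not how many. The downside is a smaller, less precise benchmark. With 10 eligible controls (assumed), the 95% margin would be 2.262 × 16.4/√10 = ±11.7, or 2.262 × 46.4/√10 = ±33.2. That is close to or above the target effect, which is why the interval should be reported with the benchmark.

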### **Primary Endpoint**

- Evaluate kinetics of viral load expressed as Ct values in nasopharyngeal swab samples over time measured at baseline (day 0), Days 3 (last day of treatment), 7, and 14 (40). The primary endpoint will be the area under the Ct curve (AUC).

The primary Phase IIa safety endpoint is the frequency of grade 3 or 4 AEs considered to be probably or definitely related to the treatment regimen.

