### 19.2.2 Efficacy

In order to compare the AUC between rintatolimod versus historical institutional benchmarks we will use the highly efficient approach proposed by Chandrasekhar et al (48). Ct values measured at baseline (Day 0), Days 3, 7 and 14 will be used to measure the AUC using a standard trapezoidal rule where the AUC for the  $i$ th subject in group  $k$  ( $k=1$  for rintatolimod and  $k=2$  for control) as  $AUC_{jk} = \sum_{i=1}^m c_j Y_{ijk}$  where  $t_1 = 0, t_2 = 3, t_3 = 7, t_4 = 14, t_5 = 30$ ,  $m = 5$ , the  $Y_{ijk}$ 's denote the corresponding Ct values per subject at the respective time points and

$$c_j = \begin{cases} \frac{t_{j+1} - t_j}{2}, & j = 1 \\ \frac{t_j - t_{j-1}}{2}, & j = m \\ \frac{t_{j+1} - t_{j-1}}{2}, & \text{otherwise} \end{cases}$$

If a Ct value is  $>40$  it will be considered right censored for the purpose of this analysis, which corresponds to a non-detectable level. We can re-express this formulation using a linear mixed model with details given exactly as in Chandrasekhar et al. (48). A large AUC value for a respective subject is a measure of treatment efficacy as compared to a subject with a lower AUC

Roswell Park Protocol No.: I-659920

value. The primary test of efficacy will be H0:  $AUC=130$  (log2 copies) x day versus H1:  $AUC>130$  (log2 copies) x day.

The secondary clinical efficacy endpoints of (i) progression of infection requiring hospitalization in patients who were not inpatients at study entry; (ii) respiratory failure requiring mechanical ventilation; and (iii) death within 30 days will be compared using Fisher's exact test. Time to a Ct value of non-detectable will be examined using an exact discrete time-to-event Cox model. The analysis of correlative endpoints will be primarily descriptive and graphical in nature.

The primary test of efficacy will be one-sided and tested at level alpha=0.05. All additional tests will be two-sided and tested at level alpha=0.05.

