## Appendix F

### Study Calendar (Main Cohort)

Baseline and/or Screening assessments must be performed within 3 days prior to the first dose of investigational product unless otherwise stated. Therapy may begin on the same day as screening. *If screening and day 1 are completed on the same day, then assessments required on both days may be done only once\**. Any results falling outside of the reference ranges may be repeated at the discretion of the investigator.

\*If screening and day 1 occur on the same day, correlative blood draw and nasopharyngeal swab collection will be as follows:

Correlative blood draw: In the case when day one of treatment is the same as the screening day, only two blood draws (30 mL each time) are needed for the correlative studies on that day: Before the start of treatment and within 1 hour after the end of the combined infusion (i.e., collect one pre-dose sample and one sample within one hour after end of rintatolimod IV, if screening and Day 1 are the same day).

Nasopharyngeal swabs: In the case when day one of treatment is the same as the screening day, only one nasopharyngeal swab (pre-dose) is required.

Evaluation	Screening and Informed Consent	Day 1	Day 3 (+ 1 day)	Day 7 (± 1 day) and Day 14 (± 3 days) 
Written Informed Consent prior to any Screening Procedures	X			
Recording of Concomitant Medications		X	X	X
Recording of Adverse Events		X	X	X
Survival Follow-up (through Day 14)		X	X	X
Clinical Assessments				
Medical & Surgical History		X		

Evaluation	Screening and Informed Consent	Day 1	Day 3 (+ 1 day)	Day 7 (± 1 day) and Day 14 (± 3 days)
Physical Exam including vital signs 	X	X	X	X
ECOG Performance Status	X	X	X	X
Laboratory Procedures				
CBC with diff	X	X	X	X
CMP	X	X	X	X
Serum hCG in women of child-bearing potential	X			
ABG	X			
Blood (30cc) for immunologic studies 	X	X (prior to treatment) and X (within 1hr after end of infusion treatment)	X (prior to treatment) and X (within 1hr after end of infusion treatment)	X 2a
Nasopharyngeal Swab (as required and based on availability)	X	X	X	X
Imaging/ Other Procedures				
12-Lead ECG	X			
CXR or CT scan 	X			

Evaluation	Screening and Informed Consent	Day 1	Day 3 (+ 1 day)	Day 7 (± 1 day) and Day 14 (± 3 days)
Clinical evaluation of endpoints 	X	X	X	X

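### The primary null AUC of 130 and the 0.80 power for 144 do not fit the plan's own Ct-AUC formula: flat Ct at the pilot baseline already gives 337 (Days 0–14) or 723 (Days 0–30)

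*Combined protocol and SAP*

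**What the plan says.** Section 19.1 makes the area under the Ct curve the Phase IIa primary efficacy endpoint, measured at baseline and Days 3, 7 and 14. Section 19.2.2 computes it by the trapezoidal rule. The text there says "Ct values measured at baseline (Day 0), Days 3, 7 and 14 will be used to measure the AUC", but the formula beside it prints m = 5 with "t_1 = 0, t_2 = 3, t_3 = 7, t_4 = 14, t_5 = 30". The values entering the sum are the Ct values themselves, and a larger AUC counts as better. The test is H0: AUC = 130 against H1: AUC > 130, one-sided at 0.05.

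Section 19.3 supplies the planning figures. Baseline Ct in 20 patients and employees "had an average of 24.1 log2 copies with a standard deviation of 6.5". Then: "The standard deviations after baseline was approximately 4.5 as the Ct values increased". The between-time-point correlation is about 0.3. On the null: "The preliminary estimate for the AUC based on our pilot data is 130 (log2 copies) x day". On power: "Given n=10 subjects we will be able to detect and increase in the AUC to an average of 144 (log2 copies) x day", at power 0.80 and one-sided alpha 0.05, assuming no censoring and compound symmetry.

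**The concern.** The figure of 130 is the threshold of the primary efficacy test, not only a planning number. A day-weighted AUC of Ct values that start near 24 and rise cannot be as small as 130 over 14 days, let alone 30. If the threshold lies far below what untreated or unchanged patients would produce, the test declares efficacy whatever the regimen does. The Phase IIa part is a single arm, so no concurrent control would expose the error. Section 2.6 says a demonstrated reduction in viral load would be the basis for a larger randomized trial. If the analyst instead uses some other scale on which 130 makes sense, the primary endpoint and its threshold are not pre-specified.

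**Working it through.** **Inputs.** From section 19.3: baseline mean Ct 24.1, SD 6.5 at baseline and 4.5 afterwards, correlation 0.3 between all pairs of time points, n = 10, one-sided alpha 0.05, null 130, alternative 144 (difference 14), no censoring. From section 19.2.2: the trapezoid weights.

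**Weights.**
- Days 0, 3, 7, 14: c = (1.5, 3.5, 5.5, 3.5), sum 14.
- Days 0, 3, 7, 14, 30: c = (1.5, 3.5, 5.5, 11.5, 8), sum 30.

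**Null value.** For a constant Ct, AUC = Ct × (sum of weights).
- Days 0–14: 24.1 × 14 = 337.4. An AUC of 130 needs a mean Ct of 130/14 = 9.3.
- Days 0–30: 24.1 × 30 = 723.0. An AUC of 130 needs a mean Ct of 130/30 = 4.3.

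Because Ct rose after baseline, 337 and 723 are floors for the pilot mean AUC. With baseline fixed at 24.1, an AUC of 130 on Days 0–14 needs a weighted post-baseline mean Ct of (130 − 1.5 × 24.1)/12.5 = 7.5, which is a fall, not a rise.

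**SD of the AUC.** With common correlation 0.3, Var = 0.7 × Σ(c·SD)² + 0.3 × (Σ c·SD)².
- Days 0–14: c·SD = (9.75, 15.75, 24.75, 15.75), so Var = 0.7 × 1203.75 + 0.3 × 66² = 2149.4, SD = 46.4, SE at n = 10 = 14.7.
- Days 0–30: c·SD = (9.75, 15.75, 24.75, 51.75, 36), so Var = 0.7 × 4929.75 + 0.3 × 138² = 9164.0, SD = 95.7, SE = 30.3.

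**Power for 144 versus 130.** By the normal approximation, power = Φ(14/SE − 1.645). The t figures use the noncentral t with 9 df.

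| Grid | Power (t / z) | Detectable difference at 0.80 (t / z) |
|---|---|---|
| Days 0–14 | 0.22 / 0.25 | 39.5 / 36.5 |
| Days 0–30 | 0.11 / 0.12 | 81.6 / 75.3 |

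The stated 0.80 is not reproduced. It would need SD(AUC) of 16.4 (t) to 17.8 (z), against 46.4 or 95.7. Zero correlation on Days 0–14 raises power only to 0.32–0.36, and higher correlation lowers it. Using SD 4.5 at every time point, which is the strict common-variance form of compound symmetry, gives 0.23–0.26.

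**Behaviour of the test.** Flat Ct at 24.1 lies (337.4 − 130)/14.66 = 14.1 SE above the null on Days 0–14, and (723 − 130)/30.27 = 19.6 SE above it on Days 0–30. Rejection probabilities on Days 0–14 for lower flat Ct values:

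| Flat Ct | AUC | P(reject), t |
|---|---|---|
| 24.1 | 337.4 | 1.00 |
| 15 | 210 | 0.9996 |
| 12 | 168 | 0.77 |
| 10 | 140 | 0.16 |

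**Other scales tried.** None is written in the plan.
- Baseline-subtracted AUC on Days 0–14: 130 is plausible (post-baseline mean Ct about 34.5), but SD is 74.7 and power 0.14–0.15.
- 40 − Ct on Days 0–14: 130 is plausible (mean Ct about 30.7), but a larger AUC would then be worse, against section 19.2.2.
- Unweighted sum of five Ct values: 130/5 = 26.0, SD 16.3, power 0.80 (t) or 0.86 (z). This fits both figures under the t calculation, but it is not an area, not in Ct × day, and not the written endpoint.

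**The case against.** The strongest reply is that 130 and 144 come from another scale on which they agree with each other. If so, there is one mismatch between the calculation and the printed formula, not two separate errors. The five-value sum shows that this is possible, and sections 2.6, 10 and 19.1 do speak of using each patient's own baseline. That reply may explain the origin, but it is conjecture. No section defines a subtraction, a rescaling or a sum, both hypotheses are stated per day, and baseline subtraction leaves power near 0.15.

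A second point is fair: Day 30 is not simply stray. The Expansion Cohort calendar in Appendix F has a Day 30 visit with a swab, so the fifth time point may have been meant for that cohort. The n = 10 test belongs to the Main Cohort, however. Its endpoint in section 19.1 and its calendar both stop at Day 14, and the null fails on either grid.

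Third, the planned analysis is a likelihood mixed model with Ct above 40 treated as right-censored, so the rejection rates here are approximations. At 14 SE this cannot change the conclusion. Censoring at 40 also concerns high Ct values, which move the AUC further above 130.

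**Conclusion.** The concern holds. On the endpoint as written, the null of 130 is less than half the AUC of patients whose Ct never leaves the pilot baseline (337 on Days 0–14), and less than a fifth on the printed Day 30 grid (723). The primary test would reject with probability about 1 under no change. Power for the stated 14-unit difference is 0.22–0.25 on Days 0–14, or 0.11–0.12 with Day 30, not 0.80. These figures rest only on section 19.3's inputs, with its two SDs combined with a common correlation of 0.3 and no censoring. Where 130 came from cannot be settled from the documents. The safety endpoints and time to non-detectable Ct do not depend on it. This must be corrected before the primary analysis.

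**What to change.** 1. **Settle one grid for the Main Cohort primary test.** Days 0, 3, 7 and 14 match section 19.1 and the Main Cohort calendar, so set m = 4 and remove the Day 30 term from this test. Otherwise, justify Day 30 and add the visit to that calendar. If Day 30 is meant for the Expansion Cohort, say so and give that analysis its own weights.
2. **Recompute the benchmark mean AUC with exactly those weights.** Use the pilot Ct series or, if it lacks Days 3 to 14, the institutional historical series mentioned in section 2.6. Restate H0 and H1 in Ct × day. On the 14-day grid the benchmark should exceed about 337, but that is a floor from the baseline mean alone and should not be adopted as the threshold. If 130 belongs to another scale, write that scale into sections 19.1 and 19.2.2 as the endpoint, with the matching direction.
3. **Restate the power or the detectable difference** for the single arm of 10 on the chosen scale.

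The cost is recalculation and protocol wording, with no added patients or procedures if n = 10 is kept. The price is a less favourable statement: about 37 to 40 Ct × day detectable at 80% power on the 14-day grid. Keeping a 14-unit target there would need about 68 (z) to 70 (t) patients, which is not proposed. Section 19.3 reports n = 20 for baseline only, so the availability of later pilot or institutional Ct values is an assumption.

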### **Primary Endpoint**

- The primary safety endpoint is the frequency of grade 3 or 4 AEs considered to be possibly, probably, or definitely related to the treatment regimen.

**Phase IIa.** The Phase IIa component of the trial is designed to be a single arm trial of IFN $\alpha$  (at MTD, if reached, otherwise at 20 MU/M) + rintatolimod along with the best available standard of care. Using each patient's baseline nasopharyngeal viral load, we will evaluate to what extent the study regimen reduces viral load relative historical institutional benchmarks. The sample size will be n=10.

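### The primary AUC test treats a pilot-estimated benchmark of 130 as a known constant, so its stated 5% error does not carry over to the claim of improvement on historical institutional experience

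*Combined protocol and SAP*

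**What the plan says.** Section 19.2.2 introduces the efficacy analysis as a comparison: "In order to compare the AUC between rintatolimod versus historical institutional benchmarks". It indexes two groups in the AUC formula, k=1 for rintatolimod and k=2 for control, and refers to a mixed model that handles censored Ct values. The hypothesis it then states has one sample: a null AUC of 130 against an AUC above 130. The level is given as "The primary test of efficacy will be one-sided and tested at level alpha=0.05".

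Section 19.3 gives the origin of the null value: "The preliminary estimate for the AUC based on our pilot data is 130 (log2 copies) x day". It says that the null hypothesis rests on this estimate, and later calls the same figure an assumed institutional benchmark. The only pilot size given belongs to baseline: "The Ct values collected at baseline for n=20 patients and employees had an average of 24.1 log2 copies with a standard deviation of 6.5". Neither section says how many people had the serial swabs needed for an AUC, or gives a standard error or interval for 130.

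For the treated group, the Phase IIa paragraph of Section 19.1 states "The sample size will be n=10" and sets the aim as viral-load reduction relative to historical institutional benchmarks. Section 2.6 likewise promises comparison with Roswell Park patients who had standard care and longitudinal viral-load monitoring.

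**The concern.** The value 130 matters only as a stand-in for what happens to institutional patients without the study drugs. It is a mean from a small sample, so it has sampling error of its own. The one-sample test counts the error in the 10 treated patients and sets the error in the benchmark to zero. If 130 happens to lie below the true institutional mean, an inactive regimen is favoured.

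Section 2.6 says that a reduction in viral load here would help to justify a larger randomized trial. A positive result would be read as improvement over institutional experience at a 5% error rate, which the stated test does not deliver. Section 19.2.2 also leaves unclear whether the analysis has one group or two.

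**Working it through.** **Inputs.** n = 10 treated (Section 19.1). Null 130, alternative 144, power 0.80, one-sided alpha 0.05 (Sections 19.2.2 and 19.3). Baseline SD 6.5; later SD: "The standard deviations after baseline was approximately 4.5 as the Ct values increased". Correlation: "The between time point correlation was estimated to be approximately rho=0.3", with compound symmetry. The pilot size m behind the AUC is not stated; m = 20 is an assumption taken from the baseline count, and I vary it.

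**1. The plan's own power figure.** Over Days 0, 3, 7 and 14 the trapezoid weights are 1.5, 3.5, 5.5 and 3.5. Weight times SD gives 9.75, 15.75, 24.75 and 15.75, with sum 66.0 and sum of squares 1203.75.

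Var(AUC) = 0.7 × 1203.75 + 0.3 × 66.0² = 842.6 + 1306.8 = 2149.4, so SD = 46.4.

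With n = 10 and a difference of 14, power is 0.22 (t) to 0.25 (z), not 0.80. Adding the Day 30 point that the formula also lists raises the SD to 95.7 and lowers power to 0.11-0.12. Power of 0.80 needs an AUC SD of about 16.4 (t) or 17.8 (z; 14 × √10 / 2.486). Among the variants tried, only an unweighted sum of five Ct values comes close (SD 16.3, t power 0.804), and that is not the stated formula. The stated power is therefore not reproduced from the stated inputs.

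**2. Scale of 130.** A Ct held flat at the baseline mean gives 24.1 × 14 = 337 over Days 0-14, and Section 19.3 says that Ct rose. An AUC of 130 over 14 days would mean an average Ct of 130/14 = 9.3. On the formula as written, the distance from the null is (337.4 − 130)/(46.4/√10) ≈ 14 standard errors, so patients with no benefit would almost always be declared a success. The next step presupposes that this has been corrected.

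**3. Error for the comparative conclusion.** Suppose the benchmark is an unbiased mean from m people with the same AUC SD. Then

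Var(trial mean − benchmark) = SD² (1/n + 1/m).

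The test uses only SD²/n, so the true SE is √(1 + n/m) times the one used, and SD cancels. The rejection rate with no effect is 1 − Φ(1.645/√(1 + n/m)), or the t version with 1.833 and 9 df. For m = 20 the ratio is √1.5 = 1.225, giving P(Z > 1.343) = 0.090 and P(t₉ > 1.497) = 0.084. A simulation of 400,000 runs gave 0.089 and 0.084.

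| People behind the benchmark, m | t | z |
|---|---|---|
| 10 | 11.4% | 12.2% |
| 15 | 9.5% | 10.1% |
| 20 | 8.4% | 9.0% |
| 30 | 7.3% | 7.7% |

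At m = 20, letting the pilot-to-trial SD ratio run from 0.75 to 1.5 gives 7.0% to 13.0%.

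**4. The average and this pilot.** These rates average over pilots that might have been drawn. At m = 20, one pilot SE equals √0.5 = 0.707 trial SEs. If 130 is one SE too low, the rate is P(Z > 1.645 − 0.707) = 17%. If it is one SE too high, it is P(Z > 1.645 + 0.707) = 0.9%.

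**5. Cost of carrying the benchmark's error.** For 10 versus 20, SE = SD × √0.15. With the SD of 16.3-17.8 implied by the stated power, SE = 6.3-6.9. Power for a difference of 14 is 0.63-0.72, and the difference detectable at 80% power is about 16-18. Restoring 0.80 for a difference of 14 with m = 20 needs about 16-22 treated patients.

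**The case against.** A fixed reference value is a common choice for a single-arm Phase IIa study, and the plan is open about it: Section 19.3 calls 130 preliminary and assumed, and Section 2.6 presents the study as groundwork for a randomized trial. That is fair, and it limits the seriousness of the point.

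A reader might infer that the true alpha of the stated test is 8-9%. The documents do not support this, for three reasons. First, the hypothesis as written concerns the constant 130, and against that constant the level is 5%. The higher figure belongs to the broader conclusion and is an average over pilots. Second, the count of 20 is attached to baseline Ct values only, so 8-9% is conditional on all 20 having contributed an AUC. Third, it assumes that 130 estimates the quantity the trial will compute, and on the Section 19.2.2 formula it does not. Nor can one say that the plan's confidence interval is too narrow, because Section 19 specifies none for the primary endpoint.

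A two-group analysis also has limits. It adds the benchmark's sampling error but cannot make pilot patients and employees comparable with treated cancer patients.

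What stands is that the plan's stated purpose is comparative, its benchmark is an estimate, and its test ignores that. Correcting the scale of 130 would not change this, because a recomputed benchmark from the same pilot would still be an estimate.

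**Conclusion.** The point holds in conditional form. For the conclusion that the regimen improves on historical institutional experience, the average one-sided error exceeds 5% for any finite pilot. It is about 8-9% with 20 people behind the AUC, 11-12% with 10 and 7-8% with 30. This assumes equal AUC SDs, an unbiased benchmark, and 130 restated on the endpoint's own scale. The direction is certain; the size is not, because the number of people behind the AUC is not reported. The scale mismatch is the larger problem and must be settled first.

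**What to change.** 1. Recompute the benchmark with exactly the AUC definition of the endpoint (same time points, weights and censoring rule). Report how many people and which swabs produced it, and its SE.
2. Make the primary test the two-group AUC comparison already indexed in Section 19.2.2 (k=1 versus k=2), with the individual pilot or historical Ct series in the same censored mixed model.
3. Reconcile the AUC SD with the formula, then restate the power or detectable difference in Section 19.3 for the actual group sizes.
4. If individual series are unavailable, use the benchmark's mean and SE in a two-sample statistic. Failing that, describe the test as one against a fixed reference value and make no 5% claim about institutional experience.

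Testing against an upper confidence limit of the benchmark is not a good substitute. With a one-sided 95% limit and 10 versus 20, the effective critical value is 1.645 × (0.316 + 0.224)/0.387 = 2.29, an alpha of about 1.1%.

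The cost is a change of SAP wording and a less favourable detectable difference. No new patients are needed to correct the error rate, but they would be needed to keep 80% power for a difference of 14. The result would still rest on the comparability of the pilot or historical group with the treated patients, and the SAP should say so.
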